COVER PAGE

Official Study Title: An Evaluation of Neurobiological Similarities of Tinnitus and Posttraumatic Stress Disorder

NCT number: NCT05981391

IRB Approval Date: 01.23.2024

Unique Protocol ID: HSC20200573HU

HUMAN SUBJECTS RESEARCH PROTOCOL

7 1. PROTOCOL TITLE: An Evaluation of Neurobiological Similarities of Tinnitus and Posttraumatic Stress Disorder

10 2. ABSTRACT

1

8 9

19

26

28

38

39

40

49

52

Past neuroimaging research demonstrates the role of the auditory system in tinnitus, which is highly comorbid and shares 11 12 symptoms with PTSD. The latest findings from a STRONG STAR neuroimaging study indicate that the auditory system is 13 also the most highly implicated resting-state brain network among individuals with combat-related PTSD (Vanasse et al., 14 2019). These findings provide a compelling argument that an underlying neurobiological mechanism contributes to comorbid tinnitus and combat-related PTSD, suggesting a different phenotype for this comorbidity. A different phenotype 15 may explain non-responsiveness to trauma-focused therapy, causing a significant public health concern. Finding 16 17 neurobiological markers of both disorders will prompt novel behavioral and neuro-modulatory therapies to target and 18 regulate specific brain networks.

To assess these conditions, we will use group information-guided independent components analysis (GIG-ICA; Du et al.,
2015; Du & Fan, 2013), a neuroimaging statistical discovery method optimized to detect between-group differences.
These analyses will determine specific brain regions within the auditory network that are common and unique to tinnitus
and PTSD; we will map these regions with corresponding symptoms. Others found a single network between the auditory
(A-1) and ventral attention (VAN) networks (Yeo et al., 2011), which explains startle responses among PTSD patients. We
will refer to this unified network as the auditory-vigilance network (A1/VAN), which will be the focus of this project.

27 3. OBJECTIVES/SPECIFIC AIMS/RESEARCH QUESTIONS

Objective:

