507 Analysis Plan: Non-inferential statistics will be calculated to include central tendencies, standard deviations, and alpha coefficients. Prior to analyzing data, unusual distributions, missing data, or outliers will be identified. Descriptive 508 509 statistics will be used to summarize participant characteristics. Group differences will be tested using t-tests, Chi-Square, or Fisher's exact tests as needed. Canonical correlations will be conducted on the data of all 60 participants from the T&P 510 and TO groups, using the subscale scores of the CAPS-5 and the TFI. Canonical correlations identify and measure 511 512 associations among two sets of variables and will identify latent variables between tinnitus-related distress and PTSD 513 symptoms. The 12 total subscales from the CAPS-5 and TFI will be entered into the analyses, requiring 60 participants for 514 large effect sizes (Steven, 1986).

515

516 Hypothesis 2a: Dysregulated connectivity within the auditory-vigilance resting state network will be implicated among

517 individuals with both tinnitus and PTSD.

- 518 Hypothesis 2b: Individuals with tinnitus and PTSD will demonstrate unique patterns of dysregulation within the auditory-
- 519 vigilance network, versus those with only PTSD, only tinnitus, and healthy controls.

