Analysis plan: rs-fMRI provides valuable information about neurobiological mechanisms that influence 520 neurological and psychiatric conditions at rest (Menon, 2011). To test our conceptual model and deduce neurobiological 521 mechanisms, we will use an existing, well-documented, 20-component parcellation scheme of the resting-state networks 522 (Laird et al., 2011; Auditory Component 16). After extracting the A1/VAN, we will use group information-guided 523 524 independent components analysis (GIG-ICA) to determine intra-network connectivity differences between those with both 525 tinnitus and PTSD, only PTSD, only tinnitus, and healthy controls. Our team (Vanasse et al., 2019) found robust 526 differences between active-duty service members with PTSD, combat controls, and civilian control (50 active-duty with 527 PTSD, 28 combat-exposed controls, and 25 civilian controls). Based on those results, 120 participants (30 per group) in 528 this proposed study, a priori power analyses demonstrated power of 80% when $\alpha = 0.05$, to detect an effect size of d = 529 0.31 (ANOVA: Fixed effects, omnibus one-way; Faul et al., 2007). Secondary analyses will examine functional connectivity between A1/VAN and other resting-state networks. 530 531

532 Hypothesis 3: Dysregulated activity within regions of the auditory-vigilance network will be correlated with symptom 533 clusters of both tinnitus-related distress and PTSD.

534 Analysis plan: Correlations will be conducted between functional connectivity within the auditory-vigilance resting state 535 network with tinnitus-related distress and PTSD symptoms. Power analyses predict that 57 participants will achieve a 536 power of .95, with an effect size d = .45, and alpha = .05 (R Core Team, 2014).

538 Missing data. If missing data can be assumed to be missing at random, likelihood-based mixed model analysis will 539 provide valid inferences using data from all cases with any outcome data. The impact of attrition on analyses will be addressed by comparing those who are available for analysis at each assessment with those who are not using 541 appropriate data from prior assessments. 542

543 6.5 Confidentiality

537

544

554

557

563

564

568

569

570

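### The 80% power for Aim 2 holds only if 0.31 is Cohen's f, and it belongs to an omnibus ANOVA that cannot establish Hypothesis 2b, for which no contrast or decision rule is named

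*Combined protocol and SAP*

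**What the plan says.** Hypothesis 2b (sections 3 and 6.4.2) is about one group set against three others: "Individuals with tinnitus and PTSD will demonstrate unique patterns of dysregulation within the" auditory-"vigilance network, versus those with only PTSD, only tinnitus, and healthy controls".

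Hypotheses 2a and 2b share one analysis plan in 6.4.2. After the A1/VAN network is extracted, the plan will use group information-guided "independent components analysis (GIG-ICA) to determine intra-network connectivity differences between those with both" conditions and the other three groups. The Abstract (section 2) calls GIG-ICA "a neuroimaging statistical discovery method optimized to detect between-group differences" and adds: "These analyses will determine specific brain regions within the auditory network that are common and unique to tinnitus" and PTSD.

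The power statement follows in the same paragraph. For 120 participants, 30 per group, "a priori power analyses demonstrated power of 80% when" alpha is 0.05. The effect size is labelled d, and the test is given as "0.31 (ANOVA: Fixed effects, omnibus one-way").

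One other sentence in 6.4.2 mentions tests between groups: "Group differences will be tested using t-tests, Chi-Square" or Fisher's exact tests. It stands in the Hypothesis 1 plan, directly after the summary of participant characteristics. It names no connectivity outcome and no pair of groups.

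**The concern.** There are two faults, of different weight.

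The lesser is the label. For four groups the omnibus calculation takes Cohen's f, the spread of the group means relative to the within-group SD. A d is a difference between two means. The two are on different scales, so a reader who takes the label at face value will misjudge the effect the study was sized for.

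The greater is that 2b has no test. An omnibus F test rejects when any of the four means differ, and its power depends only on f, not on which group stands apart. Hypothesis 2b depends entirely on which group stands apart. The plan names no contrast and no result that would count as unique to T&P. It therefore does not say how a pattern specific to T&P would be told from a PTSD effect shared with PO or a tinnitus effect shared with TO. Separating what is common from what is unique is a stated purpose of the study, and functional activity on fMRI is a primary outcome (6.4.1).

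**Working it through.** **Inputs from the documents.** Four groups, 30 each, N = 120 analysed (5, 6.1.1, 6.4.2); alpha 0.05, power 80%, effect size 0.31 (6.4.2).

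**Assumptions of this check.** One scalar connectivity measure, normal with SD 1, no covariates, pooled variance on 120 − 4 = 116 df. The patterns of means are illustrations.

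**Step 1: reproduce the stated power.** The omnibus F has 3 and 116 df, critical value 2.683 and noncentrality λ = N·f².
- 0.31 as f: λ = 120 × 0.31² = 11.53; power 81.0%. The plan's figure reproduces.
- Exactly 80% needs f = 0.3065.

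**Step 2: read 0.31 as d.** Convert with f = √[mean of (group mean − grand mean)²] at SD 1.

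| Pattern of means, range 0.31 SD | f | Power |
|---|---|---|
| Two groups at the extremes, two midway | 0.110 | 14.5% |
| One group apart from three | 0.134 | 20.0% |
| Two against two (largest possible f) | 0.155 | 25.7% |

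No reading as d comes near 80%.

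**Step 3: does the omnibus test answer 2b?** Each pattern below is scaled to f = 0.31: one group apart needs 0.31/√(3/16) = 0.716 SD; two against two needs 2 × 0.31 = 0.62 SD; equal additive effects need √2 × 0.31 = 0.438 SD each. The three-contrast rule requires T&P−PO, T&P−TO and T&P−HC all significant, each two-sided at .05, in any direction. Results are from 1,000,000 simulated sets of four means and a pooled variance per row.

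| Pattern | T&P, PO, TO, HC (SD) | Omnibus rejects | All three contrasts |
|---|---|---|---|
| PTSD effect only (2b false) | 0.62, 0.62, 0, 0 | 81% | 2.6% |
| Tinnitus effect only (2b false) | 0.62, 0, 0.62, 0 | 81% | 2.6% |
| Only HC differs (2b false) | 0, 0, 0, −0.716 | 81% | 0.6% |
| Only T&P differs | 0.716, 0, 0, 0 | 81% | 59% |
| Additive effects | 0.877, 0.438, 0.438, 0 | 81% | 23% |

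The omnibus column does not move between rows that contradict 2b and rows that do not. The three-contrast rule does separate them. With a PTSD-only effect of 2 SD its false-support rate is 5.0%, because T&P−PO is then a true null tested at .05.

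**Step 4: limits of the three-contrast rule.**
- *Additivity.* With means 2, 1, 1, 0 SD, T&P carries only the sum of the two separate effects, yet all three contrasts are significant 94.6% of the time. The interaction T&P − PO − TO + HC rejects 5.0% of the time, as it should.
- *Interaction power.* Its standard error is √(4/30) = 0.365. If only T&P differs by 0.716 SD, the noncentrality is 0.716/0.365 = 1.96 and power is 49%. The interaction also rejects 49% of the time when only HC differs by 0.716 SD, so it addresses additivity and does not replace the contrasts.
- *Several regions.* The 5% ceiling is per measure. Section 4 lists eight areas in the network. With a large PTSD-only effect in each, and independence assumed, at least one false T&P-unique region would appear with probability 1 − 0.95⁸ = 34%.

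**The case against.** **The label is a slip.** The sponsor's own 80% rules out the d reading, and the sample-size arithmetic is right once the symbol is changed. This stands. A reader might infer from the 14% to 26% figures that the study is badly underpowered; the documents do not support that, and the figures show only that the label is wrong.

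**The power sentence says omnibus, and the plan is shared with 2a.** Also true. A reader might infer that the sponsor intends to report a significant omnibus result as support for 2b. No passage says so. What the text shows is narrower: no other test is named for 2b, and no power for 2b is given.

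**ANOVA may be only the setting of the power calculation.** The plan does not specify its four-group model. Section 6.2 also plans to control for tinnitus-related distress through the TFI, while PO and HC do not endorse tinnitus, so adjusted contrasts against those groups could behave quite differently. This stands, and it is why the power figures for 2b here are illustrations and not replacement values.

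**The three contrasts are one reading of unique.** They show that T&P differs from each group, and Step 4 shows that purely additive effects can satisfy them. Whether unique means different from each group or more than the sum of the two conditions is for the sponsor to say. The fix therefore has to state what the rule shows and name the interaction for the stronger claim.

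**Testing each contrast at .05 is not safe everywhere.** The plan speaks of specific regions as well as a network. Requiring all three protects the error rate for one measure, not across many. This stands and limits the fix.

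None of these objections supplies a contrast or decision rule for 2b.

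**Conclusion.** The concern holds in two parts.

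The effect size in 6.4.2 is mislabelled. With 30 per group, 0.31 gives the stated power only as Cohen's f (81.0%); as d it gives at most 25.7%. This part uses only figures from the protocol and the pattern-dependent conversion from d to f.

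The 80% is not power for Hypothesis 2b, and the one test named for Aim 2 cannot establish 2b: at f = 0.31 it rejects 81% of the time under three patterns that contradict the hypothesis. This rests on a single unadjusted measure, but the reason is general, since omnibus power depends on f alone.

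A reader might go on to infer that 30 per group is too few. The documents do not settle that. Power for 2b depends on the rule, the measure, the covariates and the pattern of means. If only T&P differs, the three-contrast rule has about 59% power at 0.72 SD and 93% at 1.0 SD; under additive effects at f = 0.31 it has 23%. The gap is worth closing before analysis, but it is not a finding against the sample size.

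**What to change.** In section 6.4.2:

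1. Relabel 0.31 as Cohen's f, and state that the 80% applies to the omnibus test only, not to 2b.
2. Name the test for 2b: the contrasts T&P−PO, T&P−TO and T&P−HC from a four-group model, each two-sided at .05, all three required. Set no direction rule, because 2b states no direction and section 4 allows both hypo- and hyper-activation. No alpha split is needed across the three contrasts for one pre-specified A1/VAN summary measure. If the rule is applied to several regions or voxels, add multiplicity control across them.
3. State that this rule shows T&P differs from each group, and that purely additive PTSD and tinnitus effects can also satisfy it. If unique is meant as more than the sum of the two conditions, use the PTSD × tinnitus interaction as the test for that claim.
4. State power for the chosen rule under the sponsor's own assumed pattern, connectivity measure and covariates.

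The cost is a few sentences and contrast statements on the same scans and participants. The downside is a less favourable stated power for 2b. No change in sample size is requested.

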Overlapping Symptoms and Comorbidity. The same traumatic event could cause PTSD and tinnitus (e.g., IEDs). Tinnitus 61 62 can be conceptualized as a conditioned stimulus, reminding the individual of the traumatic event (Criterion B of PTSD; APA, 2013), as in flashbacks (Hinton et al., 2006). Those with tinnitus also show symptoms of avoidance (Criterion C of 63 PTSD). Veterans with both tinnitus and PTSD, and those with only tinnitus, reported similar aversions to loud signals and 64 65 lower tolerance to loud noises (Fagelson, 2007), which may result in decreased social interaction and engagement in pleasurable activities (Jastreboff & Jastreboff, 2002). Negative alterations in mood and cognition (Criterion D of PTSD) are 66 67 observed in those with tinnitus, and tinnitus-associated trauma and catastrophic cognitions predict PTSD severity (Hinton et al., 2006). Finally, individuals with tinnitus show emotional reactions that overlap with vigilance or hyperarousal 68 69 (Criterion E of PTSD), including startle responses, anger, and irritability (Fagelson & Smith, 2016), and sleep disturbance (McKenna, 2000). The high comorbidity between tinnitus and PTSD also suggests a common etiology that leads to 70 impairment and distress. Our recent study ([name] et al., 2020a) found a latent factor between tinnitus-related distress 71 72 and PTSD symptoms among veterans with PTSD, tinnitus, and posttraumatic headache. Based on this evidence, we posit 73 that PTSD exacerbates impairment among individuals with tinnitus. More research is needed to investigate psychiatric contributions to tinnitus-related distress, such as PTSD, with a possible unique phenotype when tinnitus and PTSD co-74 occur.

75 oc 76

Functional Outcomes. Functional outcomes for those with both tinnitus and PTSD are significantly worse than those with
 tinnitus only, or tinnitus and any other psychological disorder (Fagelson & Smith, 2016). This suggests a particularly
 deleterious combination of symptoms that exacerbate, and possibly maintain each disorder. It is feasible to treat
 psychiatric distress, and if successful, tinnitus-related distress will also decrease. Civilians with tinnitus had less tinnitus related distress after receiving trauma-focused therapy (Rikkert et al., 2018), but they were not evaluated for PTSD.
 These studies demonstrate the association between tinnitus and PTSD. More research is warranted to elucidate the

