114 We hypothesize that combat experiences, including stress and noise, alter functional connectivity within the A1/VAN. This 115 dysregulation contributes to tinnitus or PTSD, or both, resulting in common symptoms and clinical presentations. A1/VAN modulates hypo- and/or hyperactivity within other brain networks, resulting in symptoms of tinnitus and/or PTSD. We 116 hypothesize that the A1/VAN is a privileged network with a central role in the hypo- or hyper-activation of other networks, 117 directly or indirectly; thus, it influences tinnitus sensation, tinnitus-related distress, and PTSD. Dysregulation of specific 118 119 brain regions within A1/VAN is the neurobiological mechanism responsible for comorbid tinnitus and PTSD, and suggests 120 a different phenotype among such individuals, which may help explain high rates of non-response to PTSD treatment 121 (Steenkamp & Litz, 2020). We will examine the overlapping and unique symptoms between both disorders, the neurobiological similarity between tinnitus and PTSD, and model psychometric and neurofunctional data. 122

123 124 **5**. RESEARCH DESIGN

We propose a phenotyping and neuroimaging study, examining shared and unique symptoms and neurobiological contributions for tinnitus and PTSD. We will recruit individuals with both tinnitus and PTSD (**T&P**), PTSD Only (**PO**), Tinnitus Only (**TO**), and Healthy Controls (**HC**) (30/group). After consent is provided, participants will be scheduled for audiometric evaluations and PTSD assessment to determine eligibility. Eligible participants will be assigned to one of the four groups and scheduled for an additional tinnitus psychoacoustic evaluation, when available, to demonstrate reproducibility. Resting-state fMRI (rs-fMRI) scans will be completed at this time. Study-related procedures will be completed within 4 weeks to decrease likelihood of drop-out.

132 133

113

Figure 1. Study Design Overview.

134 135

Group Assignment Neuroimaging Assessment & Eligibility Determination **Tinnitus and PTSD** Tinnitus Psychoacoustic (T&P; N = 30)**Evaluation;** Screening; No Tinnitus, PTSD Only **Resting-State Functional Comprehensive Audiometric** Magnetic Resonance (PO; N = 30)**Evaluation;** No PTSD, Tinnitus Only Imaging (fMRI) & PTSD Assessment (TO; N = 30)**Health Controls** (HC; N = 30)

136 137

138 6. RESEARCH PLAN

139140 6.1 Selection of Subjects

141

142 **6.1.1. Subject Population.**

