6.2. Study Procedures and Description of Assessments

A trained research staff member will explain the study to potential participants in a private location and give them a copy of the informed consent document to read. The staff member will review the risks and benefits of the study and ensure the potential subject understands the research. Once consent is given, the screening assessments will then be scheduled. Timing of assessments will be determined by participants' availability. Group assignment, main outcomes, and participant characterization measures are described below. **Table 1** lists assessments.

259 Group Assignment

Participants will be assigned to one of four groups, based on results of audiometric assessments and the Clinician 260 Administered PTSD Scale for DSM-5 (CAPS-5), explained below. Those who indicate they have bothersome tinnitus and 261 262 meet criteria for PTSD on the CAPS-5 (conducted by an independent evaluator), will be assigned the Tinnitus and PTSD Group (T&P). Those who do not endorse tinnitus and meet criteria for PTSD will be assigned to the PTSD Only Group 263 264 (PO). Those who indicate they have bothersome tinnitus but do not meet criteria for PTSD will be assigned to the Tinnitus Only Group (TO). Those who do not endorse tinnitus and do not meet PTSD criteria on the CAPS-5 will be assigned to 265 266 the Healthy Control Group (HC). All will then be scheduled for an fMRI scan. Participants will be matched across groups for sex, age, head injury, length of military service, number of deployments, and hearing loss. Measures used for group 267 268 assignment and characterization are explained below.

270 Assessment Instruments.

The audiometric assessments will be conducted at the Hearing Center of Excellence (60 minutes). Repeat tinnitus acoustic assessment only (see description below) may be completed at the RII prior to the fMRI for eligible participants with tinnitus when an evaluator is available (30 minutes).

Self-report instruments may be administered at the Hearing Center of Excellence, at the STRONG STAR offices, or via
 online data capture, Clinical interviews may be administered at the STRONG STAR offices or via phone or video
 conferencing. These assessments are estimated to take approximately 90 minutes.

278

282

284

269

274

258

fMRI scans will be conducted at the Research Imaging Institute (60-75 minutes). Participants will be asked whether they

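### The only between-group test named for Hypothesis 2b cannot show that the tinnitus-plus-PTSD pattern is unique: no T&P contrast, no tinnitus-by-PTSD interaction and no definition of unique is planned

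*Combined protocol and SAP*

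**What the plan says.** Section 6.2 (Group Assignment) forms four groups from two yes/no classifications, tinnitus and PTSD. The fourth cell is explicit: "Those who do not endorse tinnitus and do not meet PTSD criteria on the CAPS-5 will be assigned to" the healthy control group. With 30 per group, this is a complete and balanced 2x2 layout.

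Hypothesis 2b in section 6.4.2 begins "Individuals with tinnitus and PTSD will demonstrate unique patterns of dysregulation within the auditory" and goes on to name PO, TO and HC as the comparators. The background (section 4) links network dysregulation to "a different phenotype among such individuals". The abstract and section 7.2 repeat the phenotype idea and offer it as a possible reason for poor response to trauma-focused therapy.

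The analysis text for 2a and 2b says that GIG-ICA will be used "to determine intra-network connectivity differences between those with both" conditions and the other three groups. The power statement then gives 120 participants, 80% power, alpha 0.05, an effect size of 0.31 labelled d, and the test "ANOVA: Fixed effects, omnibus one-way". Section 6.4.2 names no T&P contrast, factorial model or interaction, and it does not say when a pattern counts as unique. The t-tests and chi-square tests listed under Hypothesis 1 follow the descriptive statistics and are not tied to 2b.

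**The concern.** Rejecting four equal means says only that the groups are not all alike. Two further questions bear on Hypothesis 2b and its interpretation:

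- Does T&P differ from each of the other groups? This is the literal wording of 2b.
- Does T&P depart from what the two disorders would produce together? This is what a different phenotype, as opposed to co-occurrence, would need.

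The omnibus test answers neither. The second question is not academic here, because section 4 reports that the same network is implicated in PTSD and, separately, in tinnitus, with overlapping regions. Two separate effects on one network are therefore a natural competing explanation. Without a stated contrast and rule, the meaning of unique would be settled after the data are seen, and that reading would feed the discussion of treatment non-response and new therapies.

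**Working it through.** **Inputs.** From section 6.4.2: 30 per group, N = 120, alpha 0.05, effect size 0.31, one-way ANOVA with 3 and 116 df. Assumed: normal outcome, SD 1, and the mean patterns below. Means are listed in the order T&P, PO, TO, HC.

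**1. The plan's own figure.** The noncentrality is λ = N·f² = 120 × 0.31² = 11.53. With 3 and 116 df, power is 0.810, which reproduces the stated 80% if 0.31 is Cohen's f. If 0.31 were the largest gap between means in SD units, f would lie between 0.31 × √(1/8) = 0.110 and 0.31/2 = 0.155, and power would be only 14% to 26%. The figure is therefore read as f from here on.

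**2. Three patterns with the same f.** With SD 1 and four equal groups, f² = Σ(μ − mean)²/4. The interaction contrast is L = T&P − PO − TO + HC.

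| Pattern | Means | f² | Size giving f = 0.31 | L | Omnibus power |
|---|---|---|---|---|---|
| Additive | 2a, a, a, 0 | a²/2 | a = 0.31√2 = 0.438 | 0 | 81% |
| T&P only | c, 0, 0, 0 | 3c²/16 | c = 0.31 × 4/√3 = 0.716 | 0.716 | 81% |
| PTSD only (T&P = PO) | b, b, 0, 0 | b²/4 | b = 0.31 × 2 = 0.62 | 0 | 81% |

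The test cannot separate these patterns, and in the third T&P is identical to PO.

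**3. Reading unique as T&P differing from each group.** This was simulated with 30 per group, pooled variance on 116 df and three two-sided tests at 0.05, all of which must reject. Effects are exactly additive, so L = 0.

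| Effect of one disorder / the other (SD) | T&P differs from all three groups |
|---|---|
| 0.438 / 0.438 | about 23% |
| 0.5 / 0.5 | about 32% |
| 0.8 / 0.8 | about 78% |
| 0.2 / 0.6 | about 10% |
| +0.5 / −0.5 | under 1% |

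The interaction test rejects in about 5% of studies whenever effects are additive.

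**4. What 30 per group gives for the interaction.** Var(L) = 4/30, so SE = 0.365 SD and λ = L²/(4/30) = 7.5L², with 1 and 116 df.

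- 80% power needs L of about 1.03 SD (λ = 7.5 × 1.03² = 7.96).
- L = 0.716 (the T&P-only shift at f = 0.31): λ = 3.84, power 49%. Reaching 80% for this pattern would take 62 per group, 248 in total.
- L = 0.5: λ = 1.875, power 27%.

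**5. Whether the interaction alone would be enough.** Take T&P = PO = TO = 0.8 and HC = 0. T&P is then identical to both single-disorder groups, yet L = 0.8 − 0.8 − 0.8 + 0 = −0.8, λ = 4.8, and the interaction rejects in about 58% of studies. The interaction has to be combined with the T&P contrasts.

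**The case against.** A reader might infer that the plan will declare simple addition to be a unique pattern. The documents do not support that. No passage ties uniqueness to the omnibus result or to any set of pairwise tests, the ANOVA appears only in the power statement, and the phenotype language is hedged as possible. What can be said is that the rule is missing, not that a wrong rule is in place.

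A reader might also infer that the trial cannot tell a distinct phenotype from co-occurrence. That too goes beyond the documents. The interaction can be estimated from the four groups as they stand; it is simply not planned, and its precision is limited.

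Three further points have force:

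- Differing from each of the other groups is a legitimate reading of 2b. More-than-additive is a stronger requirement, which the hypothesis itself does not state. It becomes necessary only if the result is presented as more than co-occurrence.
- High omnibus rejection rates under additivity say little about 2b, because omnibus rejection does not show that T&P differs from each group. The rates in step 3 matter more. They depend on both disorders acting in the same direction with similar size, which the documents do not establish.
- Unique may also be meant spatially, since the abstract speaks of regions common and unique to the two conditions. A single scalar outcome does not model that. The contrasts and the interaction can still be applied to each regional measure, so the gap remains.

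These points narrow the concern but do not remove it. The one test named does not address 2b under either reading.

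**Conclusion.** The concern holds in limited form. Section 6.4.2 names a test that cannot support a claim of uniqueness or of a different phenotype, and it supplies neither the contrasts nor the definition that would. At the plan's own effect size, the omnibus test rejects in 81% of studies for an additive, a T&P-only and a PTSD-only pattern alike. Under the each-group reading, pure addition passes in about 23% of studies at the design effect. Across the patterns tried, the rate runs from under 1% to 78%.

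These figures rest on assumed mean patterns, SD 1, normality and a single connectivity measure. The identity of the three omnibus powers depends only on f and the group size. The point merits a change to the plan before analysis; it does not call for a different design.

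**What to change.** In section 6.4.2, keep the four-group comparison and add:

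1. The contrasts T&P versus PO, T&P versus TO and T&P versus HC, as the test of Hypothesis 2b.
2. The model connectivity ~ tinnitus + PTSD + tinnitus × PTSD, reporting the interaction with its confidence interval.
3. A claim rule. A different phenotype beyond co-occurrence is claimed only if T&P differs from both PO and TO and the interaction interval excludes zero. If T&P differs from each group but the interval includes zero, report exactly that, and say that additive effects of the two disorders are not ruled out. Do not assert additivity: with 49% power for a T&P-only shift of 0.716 SD, a non-significant interaction is weak evidence for it.
4. The interaction's sensitivity beside the existing figure: 80% power at about 1.03 SD, 49% at 0.716 SD and 27% at 0.5 SD. Relabel the 0.31 as f at the same time.

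The cost is wording only, with the same groups, data and sample size. The downside is that the stated sensitivity for the phenotype claim becomes less favourable: since the rule requires the interaction as well as the contrasts, its power cannot exceed the interaction figures above. Restoring 80% power for the T&P-only pattern would take 248 participants, which this fix does not ask for. If the investigators do not intend a more-than-additive claim, they can define unique as differing from each group and drop the stronger phenotype reading.
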